3. P-waves that occur during VVI mode during the resting and ambulatory periods for subjects with a predominant rhythm of persistent 3rd degree AV block and normal sinus node function. The device may be permanently programmed to VVI or switches to VVI mode temporarily each hour to perform a pacing threshold confirmation check and once per day to perform a pacing capture threshold test. While the device is in VVI mode AV synchronous pacing is not expected to occur in these subjects. These cycles are identified from the accuracy spreadsheet where a supplemental marker in the preceding P-P interval (column 15 (O) < P-P interval), and the pacing mode in the supplemental marker is VVI40, indicating a mode switch (column 17 (Q) = 2).

All other P-waves in the accuracy spreadsheet will be considered evaluable. Evaluable P-waves will be considered synchronous if they occur within 300 ms of the following ventricular event. Thus, evaluable P-waves will be considered synchronous if column 2 (B) ≤ 0.3 and asynchronous if column 2 (B) > 0.3 .

For the analysis of the primary objective, P-waves with records in the accuracy spreadsheet for each subject's 1-month Holter file corresponding to resting period (i.e., columns 11 (K) and 12 (L) indicate resting phase) will be selected.

A logistic regression model using generalized estimating equations, to account for the fact that the Micra AV's performance may be correlated within a study subject, will be used to construct a single estimate of the rate of AV synchrony and its 95% two-sided confidence interval across all subjects. Specifically, the outcome variable will be each successful/unsuccessful synchronous beat during the approximately 20 minutes resting period at the 1-month visit and the model will contain an intercept

term and consider observations repeated across subjects with an exchangeable working correlation structure.

A sample SAS PROC GENMOD statement for computing the overall point estimate for the algorithm's ability to provide AV synchrony and its two-sided confidence interval across all subjects is displayed below:

```
proc genmod data = AVsynchData descending;
  class pt;
  model AVsynch = / dist = binomial link = logit;
  repeated subject = pt / type = exch;
  estimate 'probability of success' int 1/ alpha = 0.05;
  output out = pred p = phat;
run;
```

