7.9.3.4 Sample Size

The MARVEL 2 study reported an average AV synchrony rate during rest of 89.2% (95% CI: 84.8% - 92.5%) with a median of 94.3% across the 40 subjects with a predominant heart rhythm of 3rd degree AV block and normal sinus node function and P-waves visible on their Holter ECG channel. The remaining subjects included 17 subjects with intact AV conduction, and 7 subjects with other predominant rhythms. Based on the distribution of predominant rhythms in the MARVEL 2 study together with the enrollment strategy described in section 5, it is expected that approximately half of the subjects with usable Holter recordings will have a predominant rhythm of 3rd degree AV block and normal sinus node function at their 1-month visit.

A simulation based on resampling with replacement from the MARVEL 2 subjects suggests that a sample size of 75 subjects with Holter recordings and with a predominant rhythm of 3rd degree persistent AV block and normal sinus node function at the 1-month visit will enable the percentage of AV synchrony to be measured with a precision (distance from point estimate to lower 2-sided 95% confidence interval) of <3.5% with 89.7% probability. Since it is expected that approximately half of the subjects with usable Holter data at the 1-month visit will have a predominant rhythm of persistent 3rd degree AV block and normal sinus node function, approximately 150 subjects with usable Holter files will be required to evaluate the primary objective. To account for the possibility of unusable Holter recordings,

unsuccessful Micra AV implant attempts, and study attrition, approximately 175 subjects may be enrolled.

Since the number of subjects that will have a predominant rhythm of 3rd degree AV block at the 1-month visit is somewhat unknown, Table 2 displays the relationship between the number of subjects that will contribute to the primary efficacy analysis and the distance between the point estimate and lower 95% confidence interval for sample sizes ranging from 40 to 90 subjects.

Table 2: Relationship Between Sample Size and Confidence Interval Width

n ¹	Median Point Estimate (%) ²	Median Lower 95% CI	Median Distance from Point Estimate to Lower CI	Probability Distance <3.5%
40	88.76%	84.83%	4.1%	37.7%
50	88.73%	85.19%	3.5%	45.2%
60	88.79%	85.58%	3.2%	63.0%
70	88.82%	85.90%	2.9%	81.9%
75	88.76%	85.87%	2.9%	89.7%
80	88.73%	85.96%	2.8%	92.9%
90	88.76%	86.13%	2.6%	98.6%

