7.9.3.7 Other Planned Analyses

As described in section 7.1.4, subjects may have different predominant heart rhythms at their 1-month and 3-month visits. For example, a subject may have intact AV conduction at their 1-month visit but have persistent 3rd degree AV block and normal sinus node function at their 3-month visit. Thus, for subjects with different predominant heart rhythms at their 1-month and 3-month visits, an estimate of percent AV synchrony will also be computed using the methods described in section 7.9.3.3 using each subject's first visit Holter recording where they have at least 500 evaluable beats and have a predominant rhythm of persistent 3rd degree AV block and normal sinus node function.

The AV synchrony percentage will also be computed using the methods described in section 7.9.3.3 for subjects not included in the primary objective analysis cohort including those subjects with intact AV conduction and other predominant rhythms.

The AV synchrony percentage during rest will also be computed using the methods described in section 7.9.3.3 among the subset of subjects with normal sinus function at 1-month with >40% ventricular pacing during the resting period regardless of AV conduction status.

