7.9.4.6 Other Planned Analyses

The AV synchrony during the 20-minutes resting periods at the 1-month and 3-months visits will be compared for subjects with predominant rhythms other than persistent 3rd degree AV block and normal sinus node function including those with intact AV conduction and other predominant rhythms, using the methods described in section 7.9.4.3.

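### Supplementary AV synchrony intervals use an uncorrected GEE method with no minimum number of subjects; if those rhythm cohorts hold about 22 subjects or fewer, the nominal 95% interval is likely to be too narrow

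*SAP*

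**What the plan says.** SAP 7.9.3.3 sets out one interval method for an AV synchrony percentage. An intercept-only logistic GEE "will be used to construct a single estimate of the rate of AV synchrony and its 95% two-sided confidence interval across all subjects". The sample code has "repeated subject = pt / type = exch" and "estimate 'probability of success' int 1/ alpha = 0.05". It requests no small-sample variance correction and no t quantile. The empirical (sandwich) standard error is not named in the text; it is the default of that code. SAP 7.9.3.3 also computes each subject's own percentage and the median across subjects.

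SAP 7.9.3.7 carries the method to further groups:

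- "The AV synchrony percentage will also be computed using the methods described in section 7.9.3.3 for subjects not included in the primary objective" cohort, covering intact conduction and other rhythms.
- "for subjects with different predominant heart rhythms at their 1-month and 3-month visits, an estimate of percent AV synchrony will also be computed", from the first qualifying visit.
- Subjects with normal sinus function and more than 40% ventricular pacing.

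SAP 7.9.5.6 carries it to the ambulatory period in other rhythms. The only stated floor is on beats: 500 per subject for the primary cohort (SAP 7.9.3.5) and for the rhythm-change estimate. There is no floor on subjects, and no cohort size is given. The wording leaves open whether intact conduction and other rhythms are pooled or estimated separately.

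**The concern.** The accuracy of a sandwich variance depends on the number of independent clusters, which here are subjects. Twenty minutes of beats per subject does not help. With few subjects the uncorrected variance is too small on average, and the normal quantile makes no allowance for having estimated it. When most subjects are near 100% and a few are far lower, a small sample often contains none of the low ones. The estimate is then high and the interval narrow at the same time, so misses tend to lie above the truth.

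The study estimates and does not test (SAP 7.1.2), so the interval is the inferential result. At stake is whether the 95% label on the supplementary rhythm-group intervals can be taken at face value.

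**Working it through.** **Inputs.** SAP 7.9.3.4 gives, for the 40 AV-block subjects in MARVEL 2, "average AV synchrony rate during rest of 89.2% (95% CI: 84.8% - 92.5%) with a median of 94.3" percent. On the other rhythms it says: "The remaining subjects included 17 subjects with intact AV conduction, and 7 subjects with other predominant rhythms". It plans about 150 usable Holters, about half of them in the primary cohort. Protocol 3.1 adds that 38 of the 40 exceeded 70% synchrony.

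**Model reduction.** With many beats per subject, the intercept-only exchangeable GEE is in effect the mean of the subject proportions. Its robust SE is SD (divisor n)/√n, and the interval is mean ± 1.96 SE on the logit scale. A beat-level GEE fit at n = 16 agreed: logit SE 0.2558 against 0.2556 from the formula.

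**Step 1: reproduce SAP Table 2.** At n = 75 the SAP states a median distance to the lower limit of 2.9%, and an 89.7% probability that the distance is below 3.5%. Three 40-point populations, fitted to Table 2, to a median near 94.3% and to 38 of 40 above 70%, give 2.9% and 87–91%. At n = 40 they give 4.1% and 33–35% (stated 4.1% and 37.7%). A smooth Beta reduced to 40 points gives 3.0% and about 92% at n = 75, but only about 15–16% at n = 40. Both bases are used below.

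**Step 2: subject-level spread.**
- SE(logit) = [logit(0.925) − logit(0.848)]/(2 × 1.96) = 0.202
- SE(p) = 0.202 × 0.892 × 0.108 = 0.0195
- SD = 0.0195 × √40 = 0.123
- Matching distribution: Beta(4.76, 0.58), median 93.7% against the reported 94.3%

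**Step 3: cohort sizes (assumptions).**
- Other rhythms, MARVEL 2 share of everyone: 150 × 7/64 = 16.4
- Other rhythms, within the plan's non-primary half: 75 × 7/24 = 21.9
- Intact conduction: 150 × 17/64 = 39.8 to 75 × 17/24 = 53.1
- All non-primary subjects pooled: about 75
- Rhythm-change group: unknown

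**Step 4: coverage of the planned interval.** Simulation with 30,000–40,000 replicates per size, ignoring within-subject binomial noise. Repeat runs differ by a few tenths of a point.

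| Subjects | Beta, predicate spread | Fitted populations |
|---|---|---|
| 75 | 94.2% | 93–94% |
| 40 | 93.4% | 91–92% |
| 22 | 92.0% | 88–92% |
| 16 | 90.7% | 87–91% |
| 10 | 88.2% | 85–90% |
| 7 | 84.9% | 83–89% |

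Under the Beta, the interval lies wholly above the truth, against wholly below it, in 6.3% and 3.0% of trials at n = 16, 8.4% and 3.3% at n = 10, and 11.2% and 4.0% at n = 7. Nominal is 2.5% each side. In the fitted populations, misses at n = 16 run about 3:1 to 5:1 on the high side.

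**Step 5: other assumed distributions at n = 16.**

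| Mean / SD (percentage points) | Coverage |
|---|---|
| 95 / 12 | 83.7% |
| 95 / 8 | 88.6% |
| 98 / 3 | 88.7% |
| 80 / 20 | 91.9% |
| 70 / 25 | 92.8% |
| 50 / 25 | 93.2%, misses symmetric |

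**Step 6: corrected interval.** In this model Mancl-DeRouen multiplies the SE by n/(n − 1); the t quantile replaces 1.96. The logit-scale width therefore grows by [n/(n − 1)] × t(n − 1)/1.96:
- n = 75: 1.0135 × 1.017 = 1.03
- n = 16: 1.0667 × 1.087 = 1.16
- n = 7: 1.1667 × 1.248 = 1.46

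Coverage with the predicate-spread Beta becomes 94.5% at 16, 94.2% at 10 and 94.4% at 7. In the fitted populations it is 91–95% at 16 and 93–97% at 7. In the 95/12 case it reaches only 88% at 16.

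**The case against.** Much of the case against a broader claim is right.

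- **Cohort size.** A reader might infer that the plan commits to cohorts of 16 or fewer. It does not. The lower figure applies the MARVEL 2 mix to all 150 subjects, which conflicts with the plan's own half share; that share gives about 22. If the non-primary subjects are pooled, there are about 75 and the problem nearly vanishes. Against this, SAP 7.1.4 lists several separate rhythm categories, and nothing sets a lower limit.
- **Borrowed distribution.** The spread comes from AV-block subjects, and the documents give no synchrony distribution for any other rhythm group. Coverage and direction are therefore conditional. A reader might infer that the intervals always flatter the device; near 50% synchrony they do not. With intact conduction, sensed beats also count towards the endpoint, so the percentage is not a pure device result.
- **Scope.** A reader might extend the point to the main ambulatory and 3-month analyses. SAP 7.9.5.4 and 7.9.4.4 draw those from the AV-block cohort, which is not expected to be small. SAP 7.9.4.6 compares visits in subjects "including those with intact AV conduction and other predominant rhythms, using the methods described in section 7.9.4.3". That is an identity-link model of a between-visit difference; it was not simulated, so no figure here applies to it.
- **Consequence.** There is no performance requirement (SAP 7.9.3.2) and no hypothesis test (SAP 7.5), and these estimates are supplementary. That limits the importance of the point, but an interval labelled 95% should still cover close to 95%.

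**Conclusion.** The point holds, conditionally, for supplementary estimates only. If a rhythm cohort has about 22 subjects or fewer and varies as the MARVEL 2 AV-block subjects did, the planned 95% interval covers about 92% at 22, 91% at 16, 88% at 10 and 85% at 7. About two thirds or more of the misses then lie above the truth. Under other assumed distributions, coverage at 16 is about 84–93%.

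A reader might conclude that the primary result is unsound. It is not: at about 75 subjects coverage is about 94% (93–94% in the fitted populations). Cohorts of 40 or more are little affected with the predicate spread (about 93% at 40), though the fitted populations give 91–92% at that size. The cohort sizes and the spread are assumptions. The absence of a correction and of a minimum number of subjects is a matter of record in the SAP.

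**What to change.** In SAP 7.9.3.3, specify the Mancl-DeRouen corrected sandwich variance with a t quantile on (number of subjects − 1) degrees of freedom for AV synchrony GEE percentages, at least for the supplementary cohorts of 7.9.3.7 and 7.9.5.6. For cohorts below about 10 subjects, report only the individual percentages and their median, which 7.9.3.3 already computes, with no model interval. State whether intact conduction and other rhythms are pooled, so that it is clear which cohorts fall under that floor.

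Kauermann-Carroll is a milder alternative, but with a t quantile it covers only about 92.8% at 7 subjects.

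The cost is SAP wording, a standard macro or package, and wider intervals: about 3% at 75 subjects, 16% at 16 and 46% at 7. Coverage may still fall short of 95% in very skewed cohorts, and the report should say so.

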7.9.4 Secondary Objective #1

Characterize the stability of AV synchrony during rest between 1-month and 3-months post implant in subjects with persistent 3rd degree AVB and normal sinus node function.

7.9.4.1 Endpoint Definition

The endpoint for secondary objective #1 will be the same as for the primary objective (see section 7.9.3.1) with the exception that ECG confirmed P-waves that occur during the 20-minute resting period at both the 1-month and 3-month visits will be included in the analysis.

7.9.4.2 Performance Requirements

There is no pre-specified performance requirement for this objective.

7.9.4.3 Analysis Methods

A Holter monitor will be placed on each subject at the 1-month and 3-month visits. Each Holter file will be processed as described in section 7.9.2 and the AV synchrony during the 20-minutes resting periods at the 1-month and 3-months visits will be compared using a generalized linear model incorporating generalized estimating equations. The response for this model on an individual heartbeat basis will be AV synchrony endpoint met as defined in section 7.9.3.1 (i.e., 1= yes, 0= no). The model will also incorporate an intercept term and indicator for visit (1-month or 3-month visits) and utilize an exchangeable working correlation structure to account for the fact that the atrioventricular synchrony may be correlated within subject. The difference in the least squared means between visits on the linear scale (i.e., when utilizing the identity link function with the binomial distribution) and its related 95% confidence interval will be used to assess the stability of the AV synchronous pacing rate between study visits.

A sample SAS PROC GENMOD statement for comparing the percentage of AV synchronous pacing between study visits is displayed below:

```
proc genmod data = AVsynchData descending;
  class pt visit;
  model AVsynch = visit / dist = binomial link = id;
  repeated subject = pt / type = exch;
  lsmeans visit / cl;
  estimate 'Difference' visit -1 1/ alpha = 0.05;
run;
```

7.9.4.4 Determination of Subjects and Data for Analysis

All subjects with persistent 3rd degree AVB and normal sinus node function and at least 500 evaluable beats during the approximately 20-minute resting period at both the 1-month and 3-month visits will be included in the analysis of this objective.

7.9.4.5 Missing Data

Similar to the primary objective, beats with no ventricular sense or pace markers and indication of telemetry dropout in the first 300 ms following a P-wave will be excluded (i.e., they are not evaluable beats). The total number of heart beats and total number of evaluable beats will be summarized for each subject and visit combination.

Additionally, a sensitivity analysis will be performed to assess the sensitivity of the estimated difference in AV synchrony percentage with respect to the missing data. Specifically, the analysis will include in the

statistical model all subjects with persistent 3rd degree AV block and normal sinus node function and at least one evaluable cardiac cycle at the 1-month and 3-month visits respectively.

7.9.4.6 Other Planned Analyses

The AV synchrony during the 20-minutes resting periods at the 1-month and 3-months visits will be compared for subjects with predominant rhythms other than persistent 3rd degree AV block and normal sinus node function including those with intact AV conduction and other predominant rhythms, using the methods described in section 7.9.4.3.

7.9.5 Secondary Objective #2

Characterize the percentage of ambulatory AV synchrony at 1-month in subjects with persistent 3rd degree AVB and normal sinus node function.

7.9.5.1 Endpoint Definition

The endpoint for secondary objective #2 will be the same as for the primary objective (see section 7.9.3.1) with the exception that ECG confirmed P-waves that occur during the ambulatory period during the 1-month Holter recording will be used in the analysis.

7.9.5.2 Performance Requirement

There is no pre-specified performance requirement for this objective.

7.9.5.3 Analysis Methods

At the 1-month visit, a Holter monitor will be placed on the subject and following the in-clinic study procedures the subject will wear the Holter monitor for approximately 24 hours as they go about their activities of daily living. The Holter files will be processed as described in section 7.9.2. A logistic regression model using generalized estimating equations will be used to construct a single estimate and 95% confidence interval for algorithm performance across all subjects using the methods described in section 7.9.3.3. For analysis purposes, the ambulatory period will be defined as starting at the end of the 20-minute resting period.

7.9.5.4 Determination of Subjects/Data for Analysis

All subjects included in the primary objective analysis cohort that have a usable Holter recording available during the ambulatory period will be included in the analysis of this objective.

7.9.5.5 Missing Data

Similar to the primary objective, beats with no ventricular sense or pace markers and indication of telemetry dropout in the first 300 ms following a P-wave will be discarded (i.e., they are not evaluable

beats). The total number of heart beats and total number of evaluable beats will be summarized for each subject.

7.9.5.6 Other Planned Analyses

An estimate of AV synchrony will also be computed for all subjects with a predominant rhythm of persistent 3rd degree AV block and normal sinus function at the 1-month visit with usable Holter recordings during the ambulatory period. This analysis will only be performed if there are subjects with a predominant rhythm of persistent 3rd degree AV block and normal sinus function at the 1-month visit that were excluded from the primary objective analysis cohort (e.g. had fewer than 500 evaluable beats during the 20 minute resting period), but have usable Holter data during the ambulatory period.

The AV synchrony percentage will also be estimated during the 1-month ambulatory period for predominant rhythms other than persistent 3rd degree AV block and normal sinus node function including those with intact AV conduction and other predominant rhythms, using the methods described in section 7.9.3.3.

7.9.6 Secondary Objective #3

Characterize the change in stroke volume, as measured by left ventricular outflow tract (LVOT) velocity time integral (VTI), during Micra AV mediated VDD pacing and VVI pacing in subjects with persistent 3rd degree AVB and normal sinus node function.

7.9.6.1 Endpoint Definition

The endpoint is LVOT VTI as obtained from echocardiogram and measured by the Echo Core Lab while the Micra AV is programmed to VDD and VVI pacing.

7.9.6.2 Performance Requirements

There is no pre-specified performance requirement for this objective.

7.9.6.3 Analysis Methods

Echocardiograms will be collected for each subject during VDD pacing and during VVI pacing within 48 hours of the Micra AV implant. To ensure that the Echo Core Lab is blinded to subject and programmed pacing mode, randomly generated numbers will be used to label the echo recording. Specifically, a random 5-digit number (“echo id”) will be assigned to label the echo recording and link the Echo Core Lab results to an individual study subject. Additionally, study sites will be randomized to perform the echo while the Micra AV system is programmed to VDD pacing first followed by VVI pacing or to VVI pacing first followed by VDD pacing. This strategy will blind the Echo Core Lab personnel to study site, subject, and pacing mode and allow the “echo id” to link to the appropriate center, subject, and pacing mode.

For each pacing mode (VDD or VVI) within each subject, up to 6 LVOT VTI and two heart rate measurements will be collected. LVOT VTI and heart rate measurements will be averaged within each subject and pacing mode combination. Subjects with at least 3 LVOT VTI measurements and one heart rate measurement in each pacing mode will be included in the analysis.

Since subject is the experimental unit, the mean difference in LVOT VTI during the VDD and VVI pacing will be estimated and tested using a paired t-test. The estimated mean difference in LVOT VIT between the two pacing modes will be reported along with its 95% confidence interval.

A sample SAS PROC TTEST statement for estimating and testing the difference in LVOT VTI during the VDD and the VVI pacing modes is displayed below:

```
proc ttest data=echo sides=2 alpha=0.05 h0=0;
  paired LVOTvtiVVI * LVOTvtiVDD;
run;
```

If graphical assessments (e.g., Q-Q plots) of the distribution of change in LVOT VTI strongly suggest a deviation from normality, the Wilcoxon Signed-Rank test may be used as a sensitivity analysis.

